### **D.3. Develop an integrated alcohol and sexual risk reduction intervention (Aim 2.a) [months 10-15]**

**a. Overview.** The purposes of Aim 2.a are (a) to use the data obtained from our formative work (Aim 1) to develop a BI with the goals of reducing at-risk drinking and sexual risk behavior, and (b) to implement this BI with 8-15 women to determine feasibility and acceptability and to obtain feedback to revise the BI in advance of further testing (Aim 3). The integrated BI will target the following: (a) reductions in quantity of drinking per occasion, binge frequency, drinking before sex, and alcohol-related consequences; (b) increases in the proportion of condom-protected sex acts, correct use of condoms, and reductions the number of partners; (c) knowledge of how alcohol use impairs decisions to have sex and use a condom, and undermines safety; and (d) how to prepare for situations in which alcohol is used (e.g., having an exit strategy, going with a friend, and bringing condoms when going to bars; protective behavioral strategies).

This intervention development and refinement will involve iterative steps: (a) Our team will review FG transcripts, identify participant-generated challenges and solutions related to alcohol use and sexual risk reduction, and incorporate them into a BI manual. (b) We will administer the BI with 8-15 women, from whom we will invite feedback during a post-BI debriefing. The team will review the feedback and interventionist notes, and suggest modifications to BI protocol throughout the pilot work. (c) We will refine the manual to reflect the lessons learned from the pilot testing. The deliverable of this aim is a fully articulated BI and manual that has demonstrated feasibility and is ready for evaluation.

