| STI                           | Chart abstraction of sexually transmitted infection   | D, O    | 1       |        |    | x     | x  |           |
|                                      | Self-report History, Testing frequency and results  | D, O    | 7       |        | x  | x     | x  |           |
|                                      | Sexual Risk Reduction Strategies  | F       | 10      |        | x  | x     | x  |           |
| Information                   | HIV and STD Knowledge Questionnaires  | O, M    | 18      |        |    | x     | x  |           |
| Norms                         | Descriptive norms for women's number of partners, condom use, partner concurrency, binge drinking   | O, M    | 6       |        |    | x     | x  |           |
|                                      | Subjective norms for binge drinking, motivation to comply, condom use, multiple partners  | O, M    | 12      |        |    | x     | x  |           |
| Attitudes                     | Attitude toward heavy drinking  | O, M    | 5       |        |    | x     | x  |           |
|                                      | Attitudes toward partner concurrency scale  | O, M    | 10      |        |    | x     | x  |           |
|                                      | Health Values   | F       | 5       |        | x  | x     | x  |           |
|                                      | Relationship Values   | F       | 23      |        | x  | x     | x  |           |
|                                      | Condom Attitudes  | M       | 26      |        |    | x     | x  |           |
| Self-efficacy                 | Self-efficacy for drink refusal (DRSEQ-R10)   | O, M    | 10      |        |    | x     | x  |           |
|                                      | Self-efficacy for condom use for each partner   | O, M    | 3xP     |        |    | x     | x  |           |
| Condom Usage                  | Assessment of Correct Condom Use  | F, O, M | 10      |        | x  | x     | x  |           |
|                                      | Condom Influence Strategy Questionnaire   | F, O, M | 8       |        | x  | x     | x  |           |
| Behavioral Intentions         | Condom use for each partner   | O       | 1xP     |        | x  | x     | x  |           |
|                                      | Multiple partners   | O       | 1       |        | x  | x     | x  |           |

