#### **D.5. Randomized Control Trial of the BI, Messaging, and Website Extenders (Aim 3) [Months 13 – 24]**

**a. Overview.** We plan a pilot study to assess the feasibility and acceptability of the BI and website, to obtain preliminary evidence of BI efficacy (on alcohol use and sex behavior outcomes), and to determine feasibility of procedures (e.g., enrollment, BI and website exposure, follow-up rates) for a future RCT.

**b. Design.** We plan a 2 (interventions) x 2 (baseline, follow-up) design. Women will be randomized, complete baseline, receive intervention (BI or brochure), post-survey (BI arm only), and 3-month follow-up. Measures will assess IMB constructs, alcohol, and sexual behavior, and STIs. Rationale for control: We chose a brochure because it is a science-based (CDC and NIAAA material) alternative that is representative of what clinics currently provide.

**c. Sample** ( $n=50$ ) was based on published guidelines for treatment development research, which recommend 15-30 per cell for Phase IB research. This also aligns with NIH expectations for R34 research. We recognize that the trial is not adequately powered to detect between-group differences, but it can clarify the potential of the intervention and suggest effect sizes (ES). We also know that ES estimates will have large standard errors. We primarily aim to find a pattern of results that is supportive of the experimental treatment.

**d. Participants.** We will recruit 50 women using screening, eligibility, recruitment, and consent procedures described in D.1.c. Women who participated in Aim 1 or 2 will not be eligible.

**e. Baseline.** Participants will complete the CASI on a tablet computer. Measures included in the CASI are listed in Table 2; the measures are reliable and valid, and have been used in prior research with young women. The CASI will take ~45 mins, and will assess background variables, outcomes, mediators, and moderators.

The self-report **outcomes** include sexual behavior; alcohol use; and the co-occurrence of sex and alcohol.

Consistent with PA-13-078, we will assess hypothesized **mediators** and **moderators**. We recognize that we will not have sufficient statistical power to test mediation or moderation in this pilot. However, we will evaluate short-term intervention effects on the hypothesized intervening variables, to determine if they have promise as potential mediators for a subsequent RCT.

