Potential **mediators** include IMB constructs: (a) information, (b) motivation, and (c) skills. To assess information we will use knowledge questionnaires. To assess motivation, we will use measures of norms, attitudes, and behavioral intentions towards alcohol use, condom use, and partner concurrency. Importantly, we will assess condom use norms and intentions by partner type; we will also assess norms, attitudes and intentions towards partner concurrency, rarely done in prior intervention studies. To assess behavioral skills for condom use we will use a measure of condom use problems and assess self-efficacy by partner.

Potential **moderators** include demographic (e.g., age, race); sexual history (e.g., number of partners, STI diagnoses, prior victimization); mental health (depression and anxiety; assessed with PHQ-9 and GAD-7); drug use (DHQ).

**f. Intervention.** Women randomized to the **control condition** will receive (after the baseline CASI) a Fact Sheet on Alcohol Use and Risks to Women’s Health prepared by the CDC. This details gender differences in alcohol intoxication, facts about alcohol use and reproductive health, pregnancy, and other women’s health concerns. Control women will then be scheduled for their follow-up session.

Women randomized to the **BI** will receive a ~45 min BI (as detailed in Table 1 and Aim 2) delivered by a health educator. After the BI, participants will be told that they will receive daily mobile messages with health facts of the day for 3 months. Women will be encouraged to visit and use the website. At the end of the BI session, women will complete a post-BI satisfaction survey, be scheduled for the follow-up. For all women, at the end of the session, the RA will thank the participant and reimburse her \$30 for completing the CASI.

**g. Process measures.** We will assess the **fidelity** with which health educators implement the **BI** by reviewing session content against a content checklist based on the manual that to obtain a % adherence score; and using blind ratings that identify behaviors consistent with MI spirit (e.g., empathetic engagement,

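### Intentions towards alcohol use are named as a measured mediator, but Table 2 has no item for them, so the pilot cannot estimate the intervention's effect on drinking intentions

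*Protocol*

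**What the plan says.** Protocol section D.5.e lists the potential mediators under information, motivation and skills. On motivation it says: "To assess motivation, we will use measures of norms, attitudes, and behavioral intentions towards alcohol use, condom use, and partner concurrency". It then adds: "Importantly, we will assess condom use norms and intentions by partner type".

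The instrument is fixed by reference. D.5.e says "Measures included in the CASI are listed in Table 2", and D.5.h points to the same table for the 3-month survey.

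In Table 2 the Behavioral Intentions block has two rows:

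- "condom use for each partner", with 1xP items (P is the number of partners), coded O (outcome);
- "multiple partners", with 1 item, coded O.

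Both are given at Aim 3 baseline and 3 months. Neither carries the code M (potential mediator or moderator).

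Section D.3.b counts the forming of risk-reduction intentions through goal-setting among the aims of the BI. Table 1 links the step of choosing alcohol and/or sexual risk goals to the establishment of an intention. Section D.5.i plans to test intervention effects on the hypothesised mediators in preparation for a larger trial.

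**The concern.** The text promises a measure that the instrument specification does not contain. Whoever programs the survey from Table 2 will ask about intentions on condoms and partners but not on drinking, in either arm.

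The BI is presented as an integrated alcohol and sexual-risk programme, and intention is one of the ways it is meant to work. The pilot's mediator data are meant to show which mechanisms are worth carrying into the full trial. With intentions measured on the sexual side only, change in drinking intentions cannot be estimated at all. A later reader could take the absence of a result as absence of an effect.

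Low power does not remove the problem. Section D.5.j puts the emphasis on effect sizes and confidence intervals, and these still need data.

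**Working it through.** The plan gives no figure to reproduce on this point. The check is a comparison of the text with Table 2, followed by a count of survey length to price the fix.

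**Step 1. Promised measures against Table 2.** D.5.e names three constructs for three behaviours, so 3 × 3 = 9 combinations. Every row cited below is marked at Aim 3 baseline and 3 months.

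| | Alcohol use | Condom use | Partner concurrency |
|---|---|---|---|
| Norms | yes: within the descriptive (6 items) and subjective (12 items) rows | yes: same rows | yes: descriptive row |
| Attitudes | yes: heavy drinking, 5 items | yes: 26 items | yes: 10 items |
| Intentions | **none** | yes: 1xP | approximate: multiple partners, 1 item |

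Seven combinations are covered, one is approximate and one is absent: 7 + 1 + 1 = 9.

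**Step 2. Could another row hold an alcohol intention?** The alcohol use, alcohol problems and protective-strategies rows are labelled as behaviour, consequences and strategies. The one other row that mentions intentions concerns pregnancy. The Behavioral Intentions block runs directly into the mental health block, and nothing suggests a row lost in extraction.

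**Step 3. What remains for alcohol.** Three rows coded M are wholly about alcohol: attitude toward heavy drinking (5), drink-refusal self-efficacy (10) and sex-related alcohol expectancies (13). That is 5 + 10 + 13 = 28 items. The two norm rows, also coded M, include binge drinking and hold 6 + 12 = 18 items, of which the alcohol share is not stated.

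**Step 4. Condom norms by partner type.** The subjective-norm row reads "Subjective norms for binge drinking, motivation to comply, condom use, multiple partners" and has a fixed count of 12. The descriptive row has a fixed count of 6. Neither states a partner-type version. Condom self-efficacy (3xP) and condom intention (1xP) are marked per partner, but xP means per individual partner, not per type. Items worded by type could sit inside a fixed count. The table does not settle it.

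**Step 5. Length of the baseline survey.** Self-report rows marked at Aim 3 baseline, leaving out chart abstraction:

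- Demographics: 13
- Alcohol use, problems and strategies: 2 + 4 + 2 + 26 + 22 = 56
- Sexual behaviour and expectancies: 9 + 13 + 13 = 35
- STI self-report and risk-reduction strategies: 7 + 10 = 17
- Information and norms: 18 + 6 + 12 = 36
- Attitudes and values: 5 + 10 + 5 + 23 + 26 = 69
- Drink-refusal self-efficacy: 10
- Condom usage: 10 + 8 = 18
- Intention, multiple partners: 1
- Mental health and drug use: 17 + 14 = 31
- Victimization: 12 + 3 + 5 = 20

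The sum is 13 + 56 + 35 + 17 + 36 + 69 + 10 + 18 + 1 + 31 + 20 = 306 fixed items. The per-partner rows add 7 + 3 + 1 = 11 for each partner.

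Added share = k / (306 + 11P), for k added items and P partners. The number of partners is an assumption:

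- P = 1: 1/317 = 0.3%; 2/317 = 0.6%
- P = 2: 1/328 = 0.3%; 2/328 = 0.6%
- P = 3: 1/339 = 0.3%; 2/339 = 0.6%

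**The case against.** The strongest reply is that this is a one-construct mismatch in a pilot of 50 women that disclaims power for mediation. D.3.b, following the Integrated Model, gives the motivational variables as attitude, perceived norms and self-efficacy, and Table 2 measures all three for alcohol. The examples of mediators in D.5.i do not name intentions. Table 2 codes no intention row M, so on the table's own terms intentions are outcomes. The SAP describes no mediator analysis. This limits the weight of the point, but it does not remove the contradiction: D.5.e names alcohol intentions among the measured mediators, and Table 2 omits them.

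Three stronger readings are tempting, and the documents support none of them.

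- A reader might infer that the alcohol side of the mechanism analysis cannot be done. It can. The five M-coded rows in Step 3 are collected at both time points.
- A reader might infer that condom norms by partner type are not measured. Condom norms are measured in both arms. Whether they are worded by type is unstated, so the finding is an ambiguity. It also belongs to the sexual-risk side and says nothing about alcohol.
- A reader might set the BI target "knowledge of how alcohol use impairs decisions to have sex and use a condom" in D.3.a against the Information row, "HIV and STD Knowledge Questionnaires", and call it a missing measure. D.3.a states what the BI aims at. On information, D.5.e promises only knowledge questionnaires, and these are listed. Their item content is not shown. Further items would be a preference.

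It might also be said that goals and readiness are discussed during the BI session. That happens in one arm only and is not a Table 2 measure, so it gives no comparison between arms.

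**Conclusion.** The point holds in a limited form. Table 2 omits one of the nine motivational measures that D.5.e promises, intentions towards alcohol use, and approximates one more. As specified, the pilot cannot estimate the BI's effect on drinking intentions, and nothing collected later can supply the missing baseline. The two intention rows that exist are coded as outcomes only, which also disagrees with D.5.e. Whether condom norms are asked by partner type cannot be told from the table.

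This rests on Table 2 being the full survey content, as D.5.e and D.5.h say, and on row labels describing what the rows contain. If the survey as programmed already holds an alcohol-intention item, the error is in the table alone.

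**What to change.** 1. In the Behavioral Intentions block of Table 2, add one or two items on intention to limit drinking and to avoid drinking before sex, at Aim 3 baseline and 3 months in both arms.
2. Code all intention rows O, M, so that the table agrees with D.5.e.
3. State in Table 2 whether the condom-norm items are asked by partner type. If they are not, amend the promise in D.5.e.

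The cost is a short edit to the survey and the table, and under 1% more items at baseline. Nothing offsets this at baseline. Shortening the 42-item Social Readjustment Rating Scale would not help there, because it is given only at 3 months. One or two new items would also lack the record of reliability that D.5.e claims for the listed measures.

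The SAP is written in the past tense, so data collection may already be complete. In that case, report that alcohol intentions were not measured and remove them from the list of assessed mediators.

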## D. 6. Timeline and Deliverables

**a. Timeline (30 months).** Months (a) 1-3: train staff, get IRB approvals, initiate screening, finalize FG materials; (b) 4-10: recruit 25 women to 6 focus groups, transcribe and analyze data (Aim 1); (c) 10-15: draft BI manual, pilot BI with ~8-15 women, get feedback, revise manual, finalize website (Aim 2); (d) 16-24: recruit 50 women to trial, analyze data (Aim 3); (e) 25-30: prepare and submit manuscripts, plan R01.

**b. Deliverables.** We will achieve these intervention development goals: (a) generate an integrated alcohol and sexual risk reduction BI, tailored to young women and partner type; (b) generate a web-delivered extender that models behavioral skills and maintains motivation; (c) demonstrate feasibility and acceptability of the BI with women in RHFP setting; (d) assess short-term change on target outcomes (i.e., condom use, number of partners, binge drinking, drinks per week); and (e) assess change in hypothesized mediators of change. These achievements will prepare us to submit a R01 to support a fully powered RCT.

## Data Analyses Plan

For the feasibility data, we produced a Consort flow figure and calculated summary statistics to report the findings. For the acceptability data, we calculated summary statistics and identified illustrative quotes from the semi-structured interviews. Prior to analyzing the efficacy data, we used t-test and chi-square analyses to determine if randomization produced equivalent groups with respect to demographic characteristics and outcome measures.

For the efficacy data, we used inferential statistics to compare the two conditions to one another. Specifically, we used generalized estimating equations (GEE; Hardin & Hilbe, 2013) to examine the impact of the intervention on primary outcomes (i.e., typical drinks per week, maximum drinks per day, number of heavy episodic drinking days, alcohol-related consequences, number of sexual partners, and alcohol use before sex) as well as to model change over time. We used an intent-to-treat approach such that data from all women were used. We hypothesized an intervention-by-time interaction such that participants in the BI, but not the control, condition would reduce alcohol use and sex risk behavior over time. All analyses examined the impact of time (baseline vs. follow-up), intervention condition (control vs. BI), and the time-by-condition interaction controlling for age. When interactions were not significant, models were run without the interaction terms. Count variables (i.e., drinks per week, maximum drinks per day, heavy episodic drinking days, number of partners, drinks before sex) were analyzed using a Poisson distribution unless otherwise indicated. Alcohol consequences were analyzed using linear models.

For condomless sex, a GEE model could not be fit due to significant over-dispersion bounded by a large number of zeroes. Instead, a zero-inflated negative binomial model was chosen based on the (a) lower AIC and BIC values in the negative binomial versus Poisson models, and zero-inflated versus non-inflated models; and the (b) likelihood ratio test comparing zero-inflated Poisson and negative binomial models (lr test:  $\chi^2(1) = 60.76, p < .001$ ) (Long & Freese, 2006). Further, a zero-inflated model is considered particularly appropriate for sexual health research, such as condomless sex (He, Tang, Wang, & Crits-Cristoph, 2014), given that some mechanisms responsible for zero counts in the data differ from

the traditional regression model. For example, women who are not engaging in any sexual activity will produce zero counts in a condomless sex outcome, no matter how they vary on other predictors, and are therefore considered to be structurally different (in statistical modeling terms) than women who are at-risk of engaging in condomless sex but do not do so. Outliers ( $z$  scores  $\geq 3.29$ ; 3 cases at baseline and 2 at follow-up) were re-expressed to the next highest value (Tabachnick & Fidell, 2007).

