To determine **feasibility** of the BI and of an RCT, we will calculate the percentage of individuals who were: eligible; consented; attended their intervention; accessed the website; and returned for the follow-up. Based on previous research, we expect  $\geq 90\%$  of those assigned to a BI to attend their intervention. Based on our recent trials (R01-MH068171), we expect  $\geq 80\%$  of all women to return for the 3-month follow-up.

To determine **acceptability** of the BI, messaging and website, we will calculate Ms for the satisfaction surveys, and inspect responses. We **predict** that the intervention materials will be well-accepted, as shown by mean ratings  $\geq 4$  on a 5-point Likert scale. To further evaluate the **acceptability** of the messaging and website, we will collect use metrics (e.g., timing and frequency of website access, number of clicks on links for information, video view time). We **predict**, and will construe as acceptable, if women receive messages, link to the website, and view videos all the way through/multiple times.

To obtain preliminary evidence of BI **efficacy**, repeated measures ANOVAs will test intervention and time effects on the primary outcomes (alcohol use frequency, quantity, binge frequency; condom use, number of sexual partners; alcohol use before sex). We **hypothesize** an intervention x time interaction for all outcomes; thus, we **hypothesize** that BI recipients but not controls will reduce alcohol use and alcohol use before sex, increase proportion of protected sex, reduce condom use problems and number of partners.

To prepare for a future trial, we also provide preliminary data on mechanisms of action by testing intervention effects on **hypothesized mediators** (e.g., IMB constructs, attitudes, norms, self-efficacy).

**j. Effect sizes and power.** We recognize that effect size estimates based on small samples often have large SDs and wide confidence intervals (CIs). We also acknowledge that we will not have power to detect statistically significant results. Nonetheless, pilot data are useful to gauge whether BI effects are encouraging, to examine distribution of outcome variables, to inform future analytic approaches, and to suggest the range of effect sizes that are reasonable to expect in a future trial. Thus, the focus of our analyses will not be on strict significance testing but on estimating effect sizes and CIs.

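### Baseline t-tests and chi-square tests cannot show that the arms are equivalent, and the efficacy models leave a chance gap in an outcome's own baseline able to shift the estimates

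*SAP*

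**What the plan says.** The SAP states that "we used t-test and chi-square analyses to determine if randomization produced equivalent groups with respect to demographic characteristics and outcome measures". It gives no significance level, equivalence margin or standardised-difference criterion, and it does not say what follows from a significant or a non-significant result.

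The efficacy models in the same section contain time, condition and their interaction, with age as the only covariate. Baseline is one of the two time points, so it enters as a response. A non-significant interaction is removed and the model refitted.

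On size, Protocol D.5.d says "We will recruit 50 women using screening, eligibility, recruitment, and consent procedures described in D.1.c". D.5.b describes two arms and two time points ("We plan a 2 (interventions) x 2 (baseline, follow-up) design"). D.5.c cites guidelines that "recommend 15-30 per cell for Phase IB research". The allocation ratio is not given.

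On inference, D.5.c says "We recognize that the trial is not adequately powered to detect between-group differences", and D.5.j says "the focus of our analyses will not be on strict significance testing but on estimating effect sizes and CIs".

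**The concern.** There are two linked problems.

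First, the tests cannot do what the sentence asks of them. After proper randomisation any baseline difference is due to chance, so a test of whether it is due to chance has no useful answer. At this sample size, silence from the test is compatible with large gaps. The approach also sits badly with the protocol, which says the trial is underpowered for between-group comparison and prefers estimates with intervals. Several of the outcomes are skewed counts, for which a t-test is a poor summary in any case.

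Second, what matters for the results is the size of the gap in each outcome's own baseline. The planned models do not remove its effect. This pilot exists partly to suggest effect sizes for a larger trial, so a chance shift of a few tenths of an SD would be carried into that planning.

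**Working it through.** **Inputs.** Total of 50 women and two arms (Protocol D.5). Assumed, because not stated: equal split (25 per arm) and two-sided 0.05. The plan gives no figure of its own for the baseline tests, so there is none to reproduce.

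**What the t-test lets through.** The smallest significant observed gap is t(0.975, n1+n2−2) × √(1/n1 + 1/n2).
- 25 v 25: t(0.975, 48) × √(2/25) = 0.569 SD.
- 27 v 23: 0.571. 30 v 20: 0.580.
- Guideline range: 0.748 at 15 per arm, 0.517 at 30 per arm.
- 25 per arm at other levels: 0.474 at 0.10, 0.759 at 0.01.

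This is a cut-off for observed gaps. A true gap of 0.57 SD would be flagged about 50% of the time, and one of 0.2 SD about 11%. A true gap of 0.81 SD is needed for 80% power.

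**Chi-square analogue.** With 5, 8, 10 or 12 of 25 in the lower arm, the smallest significant gap is 7 of 25 (28 percentage points) uncorrected, and 8 of 25 (32 points) with continuity correction.

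**Could this sample show equivalence at all?** With two one-sided tests at 0.05 and 25 per arm (normal approximation), power is zero for assumed margins of 0.2 to 0.3 SD and about 10% for 0.5 SD.

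**How often chance gives a gap.** The SE of a standardised difference is √(2/25) = 0.283. P(|gap| > 0.3) = 2 × (1 − Φ(0.3/0.283)) = 0.289 per continuous variable. The test flags 5%, so about 0.289 − 0.05 = 24% lie between 0.3 and 0.57 SD unflagged. The 0.3 is an illustrative lower end, not a threshold from the documents.

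**What a baseline gap d does to the planned estimates.** Take a continuous outcome with equal SD at both times, complete data, no true effect and baseline-to-follow-up correlation ρ. Given an observed baseline gap d, the expected follow-up gap is ρd.
- Interaction kept: follow-up gap minus baseline gap = ρd − d = −(1−ρ)d.
- Interaction dropped: the condition term averages the two gaps = (d + ρd)/2 = (1+ρ)d/2.

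No document gives ρ, so two values are shown. Absolute shifts in SD:

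| ρ (assumed) | Interaction kept, d = 0.3 to 0.57 | Interaction dropped, d = 0.3 to 0.57 |
|---|---|---|
| 0.5 | 0.15 to 0.28 | 0.23 to 0.43 |
| 0.7 | 0.09 to 0.17 | 0.26 to 0.48 |

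The two columns have opposite signs. With the interaction kept, the arm that starts higher appears to fall more. With it dropped, that arm appears worse overall.

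**Precision.** In units of the outcome variance per woman, the difference in change has variance 2(1−ρ) and the baseline-adjusted comparison 1−ρ². At ρ = 0.5 these are 1.00 and 1 − 0.25 = 0.75. At ρ = 0.7 they are 0.60 and 1 − 0.49 = 0.51.

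**The case against.** The best reply is that the baseline check is descriptive and determines no stated estimate, in a pilot that openly disclaims power. Baseline is already in the model as a response, so with the interaction kept the condition term takes up a baseline gap and the effect of interest is a difference in change. Randomisation keeps the estimators unbiased on average, and chance imbalance is already part of their standard error. At ρ = 0.5 the SE of the difference in change is √1.00 × 0.283 = 0.283 SD, so the shift in that column is at most about one SE.

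Much of this stands. A reader might infer that a baseline imbalance would go wholly unaddressed. The documents do not support that, because the repeated-measures structure handles part of it. What remains is regression to the mean while the interaction is kept, and a larger shift once it is dropped.

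A reader might also infer that the trial will declare unflagged gaps absent, or that some calculable share of trials would raise a false alarm. The SAP states no decision rule. The number of variables tested and their independence are not in the documents, so no overall false-alarm rate can be given.

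The reply does not rescue the word *equivalent*, and it gives no reason to forgo the precision from using baseline data already collected.

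**Conclusion.** The point holds as a matter of inference and of model choice. The tests cannot support a statement of equivalence: gaps up to about 0.57 SD (continuous) or about 28 to 32 percentage points (binary) pass unflagged, given an equal split of 50 and two-sided 0.05. Unequal splits of 50 barely change the continuous figure.

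The effect on the estimates is conditional on a chance gap and is not a bias on average. Its size depends on ρ, which is assumed, and on whether the interaction is kept. The figures apply to a continuous scale. The SAP fits only alcohol consequences with a linear model, so for the count outcomes they indicate the mechanism and not an exact shift.

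Deleting the tests alone would change no result. The useful gain comes from accounting for baseline by rule, which removes the conditional shift and, at ρ = 0.5, cuts the variance by a quarter relative to the difference in change. It is worth doing, but it does not undermine the feasibility and acceptability aims.

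**What to change.** 1. Delete the baseline tests and the word *equivalent*. Report baseline values by arm, with standardised differences for demographics and outcomes. Set no flagging threshold: a 0.3 SD rule, for example, would be triggered by chance in about 29% of continuous variables.

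2. Account for each outcome's baseline in its efficacy model by rule, whatever the observed gap. Either form works:
   - Keep the repeated-measures model but give the arms a common baseline mean: time, time-by-condition and age, with no condition main effect. Use a working correlation other than independence, since under independence the baseline values would contribute nothing to the adjustment.
   - Regress follow-up on condition, the outcome's baseline value and age.

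   Do not add baseline as a covariate to a model in which it is also a response.

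3. The SAP is written in the past tense. If the analysis is complete, report step 2 as a sensitivity analysis beside the existing results.

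Cost: one table, a short change to the SAP text and a small refit of each model on about 50 women. No new data are needed. The follow-up-only form drops women without a follow-up assessment, so the common-baseline form fits the SAP's intention-to-treat aim better.
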